5.4.1. Liver Chemistry Increased Monitoring Criteria

Liver chemistry stopping and increased monitoring criteria have been designed to assure subject safety and evaluate liver event etiology (in alignment with the FDA premarketing clinical liver safety guidance):
<http://www.fda.gov/downloads/Drugs/GuidanceComplianceRegulatoryInformation/Guidances/UCM174090.pdf>

Figure 4 below presents the algorithm for evaluating and monitoring liver chemistry data. It should be noted that, given TQ is administered as a single dose, there will be no opportunity to discontinue study treatment. However, liver event follow-up assessments would still apply if liver increased monitoring criteria are met.

Figure 4 Phase II Liver Chemistry Stopping and Increased Monitoring Algorithm

For further details, refer to the Liver Safety Required Actions and Follow up Assessments Section in [Appendix 2](#) (Section 12.2).

5.4.2. QTc Stopping Criteria

QTc stopping criteria will not be employed in this study.

A TQ definitive QTc study, Study TAF114582 [GlaxoSmithKline Document Number [2012N145359_00](#)], demonstrated a lack of effect on QTcF elongation at adult clinical doses (300 and 600mg). CQ does have a propensity to cause QTc prolongation; however, in TQ drug-drug interaction (DDI) Study TAF106491 [GlaxoSmithKline Document Number [WD2009/01503/00](#)] no difference was seen in PK and QTcF changes between CQ/TQ groups with all groups showing the same pattern of elongation as with CQ alone, for both frequency and magnitude of changes.

The DDI study concluded that there was no trend over time for increased QTc intervals in those treated with TQ alone. Therefore, no ECG monitoring is planned for this study.

5.5. Subject and Study Completion

A completed subject is one who attends all treatment and follow-up visits.

The end of the study is defined as the last subject's last visit.

6. STUDY TREATMENT

Chloroquine will be provided to subjects outside the parameters of this study, and according to local/national treatment guidelines. Potential subjects who are slide-positive for *P. vivax* will begin CQ treatment and sites will have 48 hours to obtain full subject consent and assent, as applicable. Consented subjects will be screened, randomized and dosed with TQ on Day 1. Two formulations of TQ will be made available; a 150 mg film-coated tablet (TQ adult tablet), and a 50mg fast-dispersing film coated tablet (TQ pediatric tablet; [Table 1](#)). Instructions for preparation and administration of the TQ formulations will be provided in the SRM.

Table 1 Study Treatments

	Study Treatment	
Product name:	tafenoquine adult tablet	tafenoquine pediatric tablet
Formulation description:	Film-coated tablet	Fast-dispersing film coated tablet
Dosage form:	Tablet	Tablet
Unit dose strength(s)/Dosage level(s):	150 mg	50 mg
Route of Administration:	Oral	Oral
Dosing instructions:	Single dose on Day 1	Single dose on Day 1
Physical description:	Dark pink capsule-shaped	Round normal concave-shaped
Method for individualizing dosage:	Subject weight	Subject weight

6.1. Treatment Assignment

This is an open-label, single arm study, and all subjects will receive CQ and TQ. Subjects will be dosed based on weight, with the goal to achieve a median TQ exposure of 96 $\mu\text{g}\cdot\text{h}/\text{mL}$, the median exposure observed in adults following administration of a 300 mg dose of TQ. The TQ doses presented in [Table 2](#) below were selected using a population PK model based on adult data and incorporation of allometric scaling.

Table 2 Tafenoquine Dosing

Weights	Tafenoquine Dose^a	Dosing Regimen
>45 kg	300 mg	2 × 150 mg or 6 × 50 mg
>40–≤45 kg	300 mg	2 × 150 mg or 6 × 50 mg
>35–≤40kg	300 mg	2 × 150 mg or 6 × 50 mg
>30–≤35kg	200 mg	4 × 50 mg
>25–≤30 kg	200 mg	4 × 50 mg
>20–≤25 kg	200 mg	4 × 50 mg
>15–≤20 kg	100 mg	2 × 50 mg
>10–≤15 kg	100 mg	2 × 50 mg
≥5–≤10 kg	50 mg	1 × 50 mg

a. The TQ dose is based on achieving a target AUC(0–∞) of 96 µg.h/ml.

The single dose of TQ will be administered at the investigator site. Subjects >35 kg have the choice of taking the TQ adult tablet or the TQ pediatric tablet. All study medication should be administered with food. If the subject vomits within 1 hour following dosing, a repeat dose should be given. If a subject sequentially vomits two doses of study medication he/she will be considered intolerant to study medication. These subjects will be withdrawn from study medication and be given appropriate rescue medication as outlined in Section 6.9.1.2.

6.2. Planned Dose Adjustments

The TQ doses and weight banding may be refined after a planned interim analysis of at least 16 subjects and based on safety and predicted exposures for the pediatric population. The observed pediatric exposure data will be compared with corresponding adult exposures that have been shown to be efficacious in order to help inform the need for any dose adjustments.

6.3. Blinding

This will be an open-label study and investigators have direct access to the subject's individual study treatment.

6.4. Packaging and Labeling

The contents of the label will be in accordance with all applicable regulatory requirements.

6.5. Preparation/Handling/Storage/Accountability

No special preparation of study treatment is required.

- Only subjects enrolled in the study may receive study treatment and only authorized site staff may supply or administer study treatment. All study treatments must be stored in a secure environmentally controlled and monitored (manual or automated) area in accordance with the labelled storage conditions with access limited to the investigator and authorized site staff.
- The investigator, institution, or the head of the medical institution (where applicable) is responsible for study treatment accountability, reconciliation, and record maintenance (i.e. receipt, reconciliation and final disposition records).
- Further guidance and information for final disposition of unused study treatment are provided in the Study Reference Manual (SRM).
- Under normal conditions of handling and administration, study treatment is not expected to pose significant safety risks to site staff.
- A Material Safety Data Sheet (MSDS) or equivalent document describing occupational hazards and recommended handling precautions either will be provided to the investigator, where this is required by local laws, or is available upon request from GSK.

Precautions will be taken to avoid direct contact with the study treatment. A Material Safety Data Sheet (MSDS) describing occupational hazards and recommended handling precautions will be provided to the investigator. In the case of unintentional occupational exposure notify the monitor, Medical Monitor and/or GSK study contact.

6.6. Compliance with Study Treatment Administration

Compliance with TQ will be assessed in all subjects by directly observing the taking of medication while at the investigator center. Despite being administered outside of this study, CQ compliance should be monitored by the site and recorded in the subject's source documentation.

6.7. Treatment of Study Treatment Overdose

An overdose for this study will be considered as any dose of study medication that is more than the planned dose on each dosing occasion.

Tafenoquine

No specific antidote for tafenoquine has been identified. In the event that overdose or toxicity does occur, individuals should be managed with appropriate supportive measures

and clinical judgement. Immediate induction of emesis and/or gastric lavage is not recommended. Hemodialysis is unlikely to be clinically useful as tafenoquine is highly protein-bound.

Methemoglobinemia has been observed in clinical trials at therapeutic doses of tafenoquine; clinically significant levels could possibly be encountered in overdose. Signs and symptoms of methemoglobinemia include (but are not limited to) blue discoloration of the skin and lips, and shortness of breath.

Chloroquine

No specific antidote for chloroquine has been identified. In the event that overdose or toxicity occurs, individuals should be managed with appropriate supportive measures and clinical judgement. Immediate induction of emesis and/or gastric lavage is not recommended.

Drowsiness, blurred vision, diplopia, blindness, tinnitus, convulsions and coma can occur with overdose. Chloroquine is a known cardiovascular toxin thus cardiac monitoring and resuscitation facilities are essential. Thus in addition to dizziness, nausea, vomiting, diarrhea and headache hypotension, cardiogenic shock and cardiac arrest may occur. The 12 lead ECG may demonstrate decreased T waves, widening of the QRS complex, which may lead to ventricular tachycardia and/or fibrillation.

In the event of an overdose the investigator should:

1. contact the Medical Monitor immediately
2. closely monitor the subject for adverse events (AEs)/serious adverse events (SAEs) and laboratory abnormalities until TQ and/or CQ can no longer be detected systemically (at least 90 days for TQ and 28 days for CQ)
3. document the quantity of the excess dose as well as the duration of the overdosing in the CRF.

Decisions regarding dose interruptions or modifications will be made by the investigator in consultation with the Medical Monitor based on the clinical evaluation of the subject.

6.8. Treatment after the End of the Study

There is no extension study planned and thus no post study treatment will be offered except for subjects diagnosed with malaria at the end of the study who will receive rescue medication outlined in Section [6.9.1.2](#).

The investigator is responsible for ensuring that consideration has been given to the post-study care of the subject's medical condition, whether or not GSK is providing specific post-study treatment.

6.9. Concomitant Medications and Non-Drug Therapies

6.9.1. Permitted Medications and Non-Drug Therapies

6.9.1.1. Concomitant Medications

All subjects can be given paracetamol during the study but administration time must be recorded in the eCRF. Allowable antibiotics are penicillins, cephalosporins, carbapenems and aminoglycosides.

All concomitant medications (prescription and non-prescription) taken during the study should be recorded in the eCRF. The minimum requirement is drug name and date of administration.

6.9.1.2. Rescue Medication

Subjects requiring rescue medication will be given appropriate medication in accordance with site (local) or national treatment guidelines for *P. vivax* malaria or; e.g., *P. falciparum* malaria, whichever is applicable. Subjects offered rescue medication should be followed up for safety assessment through the Day 120 visit to ensure resolution of the malaria infection. Details of rescue medication including reason for the rescue medication offered (e.g., withdrawal from study, treatment failure) should be recorded in the eCRF.

6.9.2. Prohibited Medications and Non-Drug Therapies

The following drugs are prohibited for use from 30 days prior to entry in the study through Day 120:

- Anti-malarials and other medicines with known anti-malarial activity (with the exception of CQ being given to potential subjects prior to randomization).

Results from an *in vitro* renal transporters study showed that TQ inhibits the renal transporters MATE1, MATE2-K AND OCT2. Inhibition of these transporters may explain mild, transient, asymptomatic increases of creatinine observed in previous clinical studies and may lead to increased exposure to medications excreted via these transporters. The following drugs are prohibited for a period of 21 days immediately following the blinded dose of TQ.

- Anti-diabetic drugs of the biguanide class:
 - Phenformin
 - Buformin
- Anti-arrhythmic drugs:
 - Dofetilide
 - Procainamide
 - Pilsicainide

Metformin, another biguanide anti-diabetic, may continue to be taken provided the subject has serum creatinine below the upper limit of normal and has no concomitant medical condition that increases the risk of lactic acidosis.

The use of herbal remedies during the course of the study is to be avoided. However, if taken this should be recorded in the eCRF under concomitant medication.

See [Appendix 7](#) in Section [12.7](#) for a non-exhaustive list of prohibited medicines for guidance.

7. STUDY ASSESSMENTS AND PROCEDURES

Protocol waivers or exemptions are not allowed with the exception of immediate safety concerns. Therefore, adherence to the study design requirements, including those specified in the Time and Events Table, are essential and required for study conduct.

This section lists the procedures and parameters of each planned study assessment. The exact timing of each assessment is listed in the Time and Events Table (Section [7.1](#)).

7.1. Time and Events Table

Protocol Activity	Visit Day									
	Screen & Treat	Follow-Up Period							Recurrence Visit ^a	Withdrawal Visit ^b
	Day 1 ^c	Day 3	day 8	Day 15	Day 29	Day 60	Day 90	Day 120	Recurrence	Withdrawal
Window		+2d	-/+2d	-/+3d	-/+5d	-/+10d	-/+10d	-/+10d		
Informed Consent Process	X									
Demographic Information	X									
Initial History Only ^d	X									
Physician Assess. Malaria Signs & Symptoms	X									
Inclusion/Exclusion Criteria	X									
Efficacy Assessments										
Parasitological Assessment (blood smear)	X		X		X	X	X	X	X	X
Plasmodium PCR genotyping	X								X	
Safety Assessments										
Review Concomitant Medications	X	X	X	X	X	X	X	X	X	X
Vital Signs ^{e,f}	X	X		X	X	X			X	X
Brief Physical Examination ^f	X	X	X		X	X	X	X	X	X
Adverse Events Assessment ^g	X	X	X	X	X	X	X	X	X	X
Serious Adverse Events ^h	X	X	X	X	X	X	X	X	X	X
G6PD (phenotyping) ⁱ	X									
G6PD (genotyping)					X ^j					
Ophthalmological Exam (qualified site only)	X							X		X

Protocol Activity	Visit Day									
	Screen & Treat	Follow-Up Period							Recurrence Visit ^a	Withdrawal Visit ^b
	Day 1 ^c	Day 3	day 8	Day 15	Day 29	Day 60	Day 90	Day 120	Recurrence	Withdrawal
Window		+2d	-/+2d	-/+3d	-/+5d	-/+10d	-/+10d	-/+10d		
Laboratory Assessments										
Hematology ^k	X	X	X							
Clinical Chemistry ^l	X		X							
Methemoglobin	X		X							
Pregnancy Test ^m	X				X	X	X		X	X
Pharmacokinetic Assessments										
Pharmacokinetic Sampling		X ⁿ		X ^o	X ^o	X			X	
Investigational Product										
Dispense Open Label tafenoquine	X									
Treatment Compliance Int. - Invest.	X									
IVRS Registration	X									

- a. Subjects who have a recurrence will continue to be monitored for safety and efficacy at all scheduled visits through day 120. Recurrence is defined by a positive blood smear with or without vivax malaria symptoms.
- b. If a subject withdraws, the site should offer to conduct safety assessments through Day 120.
- c. Visit Day 1 includes all screening procedures and treatment with tafenoquine.
- d. Includes medical, disease and therapy histories.
- e. Vital signs include height and weight (screening only), blood pressure, temperature, heart rate and respiratory rate. Refer to Section 7.5.4 for additional details.
- f. At Center PPD, Vital Signs and Brief Physical Examination will be performed at every visit.
- g. Adverse events are recorded from the time of the first dose of study medication.
- h. Serious adverse events are recorded from the time of consent in order to fulfil international regulatory requirements.
- i. G6PD phenotyping to be performed by quantitative spectrophotometric analysis. One or more G6PD rapid point of care tests may be performed at baseline (Day 1) only.
- j. A blood sample for G6PD genotyping will be collected only from subjects who experience a SAE due to hemoglobin decline. Subjects with hemoglobin decline should continue to attend all visits through Day 120 to monitor Hb status.
- k. Hematology includes hemoglobin, hematocrit, red blood cell/white blood cell/platelet counts, mean cell volume, white blood cell differential and reticulocyte count.
- l. Clinical Chemistry includes CPK, BUN, serum creatinine, total and indirect bilirubin and liver clinical chemistry.
- m. Pregnancy testing is only for females of child-bearing potential. Use a urine pregnancy test that is routinely used at the site with a test sensitivity for human chorionic gonadotropin (hCG) level ≤ 25 mIU/mL.
- n. Day 3 PK sample must be taken 24-96 hours post TQ dose.
- o. Once full PK sampling has completed, remaining enrolled subjects will provide two PK samples at Day 15 and Day 29.

7.2. Screening and Critical Baseline Assessments

Study site personnel must obtain written, dated informed consent from the parent(s) or legal guardian(s) of the subject, as well as assent from the subject, if applicable, prior to the initiation of any screening procedures.

The following clinical and laboratory assessments will be conducted at screening (prior to the dose of TQ) as detailed in the Time and Events (Section 7.1):

- Demographic data will be collected to include details of date of birth, gender, race and ethnicity
- Medical history will be collected, including medical, disease and therapy histories; and, cardiovascular history and associated risk factors
- A brief physical examination will be conducted including:
 - Cardiovascular examination
 - Abdominal examination including assessment of splenomegaly
 - Respiratory examination
- Vital signs will be assessed. These include height, weight, temperature (oral, axillary or tympanic), heart rate, respiratory rate, systolic and diastolic blood pressure
- Investigators will assess *P. vivax* malaria symptoms at baseline. The incidence and severity (defined as absent, mild, moderate, severe, or unknown) of the following symptoms will be recorded: chills and rigors, headache, dizziness, abdominal pain, anorexia, nausea, vomiting, diarrhea, pruritis or itching, and coughing. The date of onset of symptoms will also be recorded. The investigator or designee can also assess and record any other *P. vivax* malaria symptoms.
- Blood smears for parasitological assessment will be collected and examined for the presence of Plasmodium species asexual parasites and gametocytes (see Section 7.4 and the SRM for further details). Given the subject may have already received one or more doses of CQ, the parasitological assessment at Day 1 may be negative.
- A blood sample will be collected on filter paper and stored for future plasmodium genotyping analysis.
- Current and prior medications will be reviewed including any anti-malarial medication that has been used.
- G6PD status will be assessed using quantitative spectrophotometric analysis (further instructions can be found in the SRM). The quantitative analysis will be used to determine the subject's eligibility for the study. One or more G6PD rapid point of care tests may also be performed at baseline.

- Periodic external quality assurance testing will be performed to ensure high quality G6PD assay data. Procedures for quality assurance will be described in detail in the SRM.
- The following laboratory assessments will be performed by local laboratories at screening and prior to dosing TQ:
 - Hematology analysis will include: Hb, hematocrit (Hct), red blood cells (RBC), white blood cells (WBC), mean cell volume (MCV), differentiated WBC, platelets and reticulocytes (for conversion to absolute).
 - Clinical chemistry evaluations will include: blood urea nitrogen (BUN), serum creatinine, total and indirect bilirubin and liver chemistries (alanine aminotransferase (ALT), aspartate aminotransferase (AST), alkaline phosphatase (ALP) and creatine phosphokinase (CPK)).
- A urine pregnancy test will be performed on females of childbearing potential that is routinely used at the site, provided the test has sensitivity for human chorionic gonadotropin (hCG) of ≤ 25 mIU/mL.
- Methemoglobin levels will be assessed using a non-invasive signal extraction CO-Oximeter handheld machine.
- Center ^{PPD} (Manuas, Brazil) only will perform the following ophthalmic assessments prior to randomization:
 - Visual acuity will be assessed by standard methods
 - Slit lamp examination of the cornea to evaluate for vortex keratopathy
 - Retinal digital imaging (color photographs, fundus autofluorescence and OCT)

7.3. **Unscheduled Visits**

Subjects who have one or more visits outside the allowable time window defined for each scheduled visit will undergo all the procedures and assessments described in the Time and Events Table (Section 7.1) with the exception of assessments performed only at screening and the PK assessments. Subjects should be able and/or encouraged to return to the clinic for unscheduled visits at anytime during the 120-day study period. In addition, subjects must return to the clinic anytime they are experiencing a recurrence of malaria symptoms.

7.4. **Efficacy**

The study is not powered to produce precise estimates of efficacy. However, the estimates of recurrence-free efficacy at Day 120 will be reviewed at each interim and at the final analysis of the study. The doses in the pediatric study (Section 6.1) have been selected to match the exposure following an efficacious dose of TQ (300 mg) in adults,

and are therefore expected to provide similar levels of efficacy in the pediatric population.

Parasitology

Microscope blood slides will be prepared pre-dose at screening on Day 1 to confirm the presence (positive or negative) of *P. vivax* malaria (asexual parasites and gametocytes), and on Day 8 to confirm the parasite has cleared. Blood films will also be prepared during follow-up on Days 29, 60, 90 and 120. In addition, blood films should be obtained at the recurrence visit or withdrawal visit as applicable. At each time point two thick and one thin film slides should be prepared on separate slides and one additional unstained slide with both thick and thin films retained for quality control. For detailed instructions on the methodology for staining please refer to the SRM.

Parasite Genotyping

Two drops of peripheral blood will be collected onto pre-printed filter paper for subsequent DNA extraction and genetic analysis of Plasmodium species on all subjects on Day 1, prior to TQ dose and; if necessary, at the time of the first recurrence.

Analysis of the *P. vivax* genes, such as *PvMSP-1*, *PvCSP* and *PvAMA-1*, as well as any other markers deemed appropriate, will be used to distinguish between genetically homologous and genetically heterologous infection.

External quality control

External quality control of slide readings will be conducted by an independent laboratory. They will examine a proportion of slides from each study site. The procedure for quality control will be described in the SRM.

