7.6. Pharmacokinetics

Blood samples for PK analysis of TQ will be collected at the time points indicated in the Time and Events Table (Section 7.1). The Day 3 sample should be taken 24-96 hours after TQ dosing and a concurrent set of vital signs should also be obtained. Sample(s) of 1 mL blood will be collected (via venipuncture) into blood tubes and/or 70 µL blood (via finger or heel prick) will be collected into capillary tubes. Each sample will be centrifuged to produce plasma and the plasma transferred into a tube for shipping to a central laboratory for analysis. The actual date and time of each blood sample collection will be recorded. The timing and collection of PK samples may be altered and/or PK samples may be obtained at additional time points to ensure sufficient PK monitoring. In addition, concentrations of CQ will be determined. Details of the PK blood sample collection (both venipuncture and microsampling), processing, storage and shipping procedures are provided in the SRM.

Evaluation of correlation between venous and microsampling data will be made at each interim analysis. If microsampling data is deemed adequately representative of venous blood samples, any further PK sampling will switch predominantly to microsampling. However, up to two out of the four planned PK samples per subject may still be collected by both venous and microsampling methods. This will be as a back-up given the primary objective of this study is to adequately characterize the PK of TQ in the pediatric population. The PK data hence is of critical value. In the event that microsampling data is deemed an inadequate representation of venous samples, any further PK sampling will be only by venous sampling.

The sampling strategy of four PK samples per subject is designed to be sparse but adequately characterize the PK of TQ in the pediatric population. These four samples per subject will be reduced to two samples per subject at the earliest interim analysis once reliable characterization of TQ PK has been achieved.

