9. STATISTICAL CONSIDERATIONS AND DATA ANALYSES

9.1. Hypotheses

There are no hypotheses tested in this study. The study is designed to characterize the TQ exposures in pediatric subjects.

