9.2.1. Sample Size Assumptions

A population PK modelling and simulations-based approach was utilized to support appropriate study sample size and PK sampling times for the proposed population PK bridging study. Based on these simulations, a sample size of 16 subjects and a sparse sampling scheme of four time points per subject (Day 3 (24 to 96 hours post TQ dose), Day 15, Day 29, and Day 60) are considered sufficient for the evaluation of the primary PK objective of estimating exposure within each weight band in pediatric subjects aged ≥ 2 years to < 16 years.

Assuming that the rates of absorption and distribution in this population will be similar to the adult population, this sparse sampling scheme allows for adequate estimation of TQ clearance (coefficient of variation $< 40\%$ within each weight band as per regulatory recommendation) and thereby exposure within each weight band while obtaining a minimum number of samples for each subject ([Appendix 9](#), Section 12.9).

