10.13.6. POP PK File Specification

10.13.6.1. Pop PK Dataset File Structure

The PME compliant file structure for pop PK is a space-delimited file with each row containing the following columns of information. This file will be provided within 5 days of DBF.

Records with CONC value of NS, IS or NR will be excluded from the dataset

Item Name	Description	Code	Derivation/Comments	Dataset
ID	NONMEM sequential number starting at 1 identifying each subject	00001 – 99999	Sequential identifier for each subject starting at 1.	
CENT	Centre Identification	1= Thailand - PPD 2= Madagascar - PPD 3= Peru - PPD 4= Thailand - PPD 5= Vietnam - PPD 6= Brazil - PPD 7= Colombia - PPD 8= Thailand - PPD 9= Thailand - PPD 10= Vietnam - PPD 11=USA - PPD 12= India- PPD 13= Philippines- PPD 14= Brazil- PPD 15=Ethiopia- PPD 16= Ethiopia- PPD 17=Cambodia PPD 18=Brazil- PPD 19=Peru PPD 20=SMIU Thailand- PPD 21=Thailand- PPD 22=Vietnam- PPD 23=Colombia- PPD 24=Colombia PPD	Additional centre numbers to be added based on where patients are recruited	
PT	Patient Identification Number		As per randomization; Retain all subjects with at least one measurable PK sample for the TQ analyte(s)	
STUDY		6= TAF113577		
TRTGRP	Treatment group for each study	24: TAF113577 arm		

Item Name	Description	Code	Derivation/Comments	Dataset
HEALTHY	Healthy volunteer or patient	1: Healthy volunteer 2: Patient	Studies 200951, 201780 and TAF114582 are all in Healthy volunteers (i.e., HEALTHY=1)	
DOSE	Dose amount (mg) for tafenoquine (TQ, SB252263)		Fill in the intended dose amount (mg) in all cells for each patient.	TQ
AMT	Dose amount (mcg) for tafenoquine	If EVID=1, AMT= Dose amt in mcg for tafenoquine If EVID=0, AMT= 0		TQ
DAY	Study day relative to the start of study		Day = day of study relative to the TQ dose	
DATE	Date of dose or sample collected.	MM/DD/YYYY		
TIME	Time of dose sample collected.	HH:MM (24 hr)		
RTLDD	Relative time of sample from most recent TQ dose (hr)	Numeric	If negative assign 0	
RTFD	Relative time of sample from first TQ dose (hr)	Numeric	If negative assign 0	
TQ	Plasma TQ concentrations (ng/mL)	Numeric If EVID = 1, DV = "." If CODE > 0 then DV = "." Else DV= conc. Value Where ADPC .AVAL ne "" or ADPC.ANL01FL="Y" Then TQ=ADPC.AVAL	3 decimal places.	TQ
LNTQ	Ln transformed Plasma TQ concentrations	Numeric	6 decimal places.	TQ
CODE	Drug concentration result code	0 = Measurable conc. 0 when EVID=1 1 = NQ/BQL 2 = NA/NR/NS/IS		

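### Protocol Section 7.3 bars PK sampling at out-of-window visits, Section 7.6 allows it, and following 7.3 loses planned primary-endpoint samples that the model could use (minor)

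*Protocol*

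**What the plan says.** Protocol Section 7.3 (Unscheduled Visits) covers subjects with one or more visits outside the allowable window. They have all Time and Events procedures "with the exception of assessments performed only at screening and the PK assessments". Section 7 allows no waivers except for immediate safety concerns. Section 5.4 tells sites to re-schedule a missed visit as soon as possible, so late attendance is foreseen.

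Section 7.6 is more permissive: the timing of PK samples may be altered, and samples may be taken at additional time points. It does not say who decides. It also says of this study: "The PK data hence is of critical value". The Time and Events Table has a PK sample at the recurrence visit, whenever that falls.

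Full sampling is four samples per child. After it stops: "Once full PK sampling has completed, remaining enrolled subjects will provide two PK samples at Day 15 and Day 29".

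Actual times are available to the analysis. Section 7.6: "The actual date and time of each blood sample collection will be recorded". The population PK file (SAP 10.13.6.1) carries date, clock time and hours since dose. SAP 10.13.3.1 deletes concentrations when dosing or sampling times are missing; no rule was found that deletes them for being out of window.

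The PK population is worded in two ways. Protocol Section 9.3.1 joins Days 3, 15, 29 *and* 60; SAP Section 4 joins them with *or* and requires accurate dosing and sample times. SAP 10.3.1 applies visit windows to PK (Day 15 is Days 12-18, Day 29 is Days 24-34). SAP 10.13.6.1 retains every subject with at least one measurable TQ sample.

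**The concern.** A child who comes on Day 36 for the Day 29 visit is two days past the window. Under 7.3 the site takes a smear, vital signs and the rest, but no PK sample. Under 7.6 it could take one. Two sites could act differently on the same facts, and the one that follows 7.3 literally gives up a planned sample for the primary endpoint, AUC by weight band, for no reason that the analysis requires.

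The loss weighs most on a child in the two-sample phase, where one missed sample is half of that child's PK data. The *and*/*or* wording and the SAP windows add a second doubt: if a late sample is taken, does it count towards the PK population?

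**Working it through.** **1. Reproducing the model.** Inputs from Protocol Appendix 9, Table 7: A 0.8586, B 0.4813, Alpha 0.4380, Beta 0.0415, KA 3.3073 (rates per day); log-SDs 0.2766 (A and B), 0.1695 (Beta), 0.2657 (residual).

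AUC per mg = (A/Alpha + B/Beta − (A+B)/KA) × 24/1000 = (1.960 + 11.598 − 0.405) × 0.024 = 0.316 µg·h/mL/mg, the figure in Appendix 8. At 300 mg this is 94.7, and 94.7 × exp(±1.96 × 0.2766) gives 55.1 to 162.9, against 55-162 in the plan.

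A simulation of 3000 children (Appendix 9 weights and doses), estimating each child's AUC from both random effects with population parameters treated as known, gives an AUC RMSE of 13.5 µg·h/mL for Days 3, 15, 29, 60 and 16.5 without Day 60. Table 9 (n=16, unstratified) gives 13.2 and 15.8, though its three-sample run also fixes one variance. Agreement is close enough to compare schedules.

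**2. When a visit is out of window.** From the visit windows and the Day 3 rule of 24-96 hours, PK windows are Days 2-5, 12-18, 24-34 and 50-70: 4 + 7 + 11 + 21 = 43 of the 69 days from Day 2 to Day 70. Days 6-11, 19-23 and 35-49 lie outside.

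**3. Effect on one child, two-sample scheme.** RMSE of log(estimated AUC / true AUC), from two separate simulations; dose cancels on this scale:

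| Samples obtained | 1500 children | 3000 children |
|---|---|---|
| Days 15 + 29 | 0.163 | 0.160 |
| Day 15 only | 0.217 | 0.212 |
| Day 29 only | 0.196 | 0.198 |
| Day 15 + late second sample | 0.158 (Day 36) | 0.157 (Day 40) |
| Days 20 + 36 | 0.157 | not run |
| None | 0.320 | 0.313 |

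Losing one sample: 0.217/0.163 = 1.33 and 0.196/0.163 = 1.20, so error rises 20-33%. A late sample removes the loss; differences of a few thousandths are simulation noise.

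**4. Effect on one child, four-sample scheme.** AUC RMSE goes from 13.5 to 15.0 (Day 15 or Day 29 lost, +11%) or 16.5 (Day 60 lost, +22%). With Day 15 taken at Day 21 it is 12.8; with Day 60 taken at Day 45 or Day 75 it is 13.1 or 12.8. A displaced Day 3 sample was not tested.

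**5. How many children.** The two-sample scheme covers at most 60 − 16 = 44 children, or 60 − 32 = 28 if full sampling runs to 32. The documents give no out-of-window rate; assume p = 5%, 10%, 20% per PK visit, independent.

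- At least one sample lost, 44 × (1 − (1 − p)²): 4.3, 8.4, 15.8 children.
- Both lost, 44 × p²: 0.1, 0.4, 1.8 children.

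**6. Effect on the endpoint itself.** The standard error of population log-AUC was computed at the band mid-points 7.5, 15, 27.5 and 47.5 kg from a first-order information matrix: Table 7 values; Alpha, KA and the A:B ratio fixed; Appendix 9 weights; 16 children on four samples and 44 on two. If 5%, 10% or 20% of all PK samples are lost, it rises about 1%, 2% and 5%. At 7.5 kg, the least precise band, it goes from 0.106 to 0.107, 0.108 and 0.112. Protocol Section 9.2.1 asks for a clearance CV below 40% in each band.

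**The case against.** The strongest case against is that this is a wording conflict with little consequence. Section 7.6 already gives a route to an off-schedule sample, recurrence visits already have PK, the windows are wide, and Section 9.3.2 wants blood draws in children kept to what is needed. Appendix 9 concludes that the number of samples matters little if the terminal phase is sampled. Most of this stands, and step 6 bears it out. Two parts do not. Section 7.6 says only that samples may be taken, while 7.3 tells sites to leave them out. And Table 9 tests no scheme with fewer than three samples, so it does not show that a two-sample child can lose one without cost.

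A reader might infer more than the documents support:

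- *That data are discarded.* The samples are not collected; no rule was found that drops a collected sample for its timing.
- *That the primary analysis is at risk.* Precision by weight band stays far inside the 40% target.
- *That late attenders bias the result.* The documents say nothing about who attends late.
- *That infants bear most of the loss.* SAP 10.13.4.2 says four-sample collection may continue in those aged 6 months to 2 years, and in the lowest weight band.
- *That the protocol's* and *requires a sample on every listed day.* Of 16 children, 16 × (1 − p)⁴ = 13.0, 10.5 or 6.6 would then remain evaluable at p = 5%, 10%, 20%. But that reading would exclude every two-sample child by design, so it cannot be meant. The wording still needs correcting.

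**Conclusion.** The point holds as a minor one. Sections 7.3 and 7.6 give different answers on PK at an out-of-window visit, and following 7.3 loses a planned sample without analytic reason. The cost is clear for an individual two-sample child (log-AUC error up about 20-33%, recovered by a late sample) and small for AUC by weight band (standard error up about 1-5%). Few two-sample children would lose both samples.

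The counts and the band-level figures rest on assumed loss rates of 5-20%. The individual errors treat the adult population parameters as known, so the comparison between schedules is more reliable than the absolute values.

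**What to change.** Amend Protocol Section 7.3: if a scheduled PK sample has not yet been taken, collect it at the out-of-window visit and record the actual date and time; no child gives more samples than planned. Say whether this extends to the Day 3 sample, which has its own rule ("Day 3 PK sample must be taken 24-96 hours post TQ dose"). Cross-refer to Section 7.6 so that the two agree.

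Align Protocol Section 9.3.1 and SAP Sections 4 and 10.3.1 so that any post-dose sample with accurate dose and sample times counts towards the PK population, assigned by actual time. This matches the retention rule already in SAP 10.13.6.1.

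The cost is a sentence or two in each document, and for some children a blood draw at an off-schedule visit in place of the one they missed.
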